7.3 Interim analysis

An interim analysis summarising both efficacy and safety will be performed when all subjects enrolled in the ePHex-OLE study have 12 months data.

7.4 Subject and study disposition

Unless stated otherwise, all data will be listed.

7.4.1 Inclusion/exclusion criteria

A summary table (percent and frequency) of subjects violating inclusion/exclusion criteria will be presented.

7.4.2 Disposition

An overview table will be created, stating the number and percentage of subjects per site, including country and site number and investigator name.

Subject disposition will be presented with a summary of the number/percentage of subjects treated, completed, and reasons for non-completion, per treatment group and overall. Additionally, in the same summary, the number/percentage of subjects in the FAS and the SAF will be presented. Number and percentage of subjects included in the applicable subgroups will be presented, plus descriptive statistics on follow-up time, calculated from first treatment dose in the ePHex-OLE study.

The listing to be created will include on a per-subject level the reasons for withdrawal of both study and/or treatment, as well as information on WIC date and center/site. Follow-up time for each subject calculated from first treatment dose in the ePHex-OLE study will also be presented.

7.4.3 Protocol Deviations

Important protocol deviations, as agreed prior to database lock, will be summarized according to their classification. All protocol deviations will be listed.

7.5 Baseline characteristics

Both baseline characteristics in the ePHex study and in the ePHex-OLE study will be described for the subjects enrolled in the ePHex-OLE study.

Baseline characteristics will also be described for subjects included in the FAS of the ePHex study, but not participating in the ePHex-OLE study.

7.5.1 Demographics

Data (including weight, height and BMI measurements at screening) for FAS and SAF per treatment group and overall will be summarized, using metric units where applicable (see section 11.1 for reference to addendum). Appropriate descriptive statistics for age, height, weight, BMI, race and sex will be given.

Demographics in the ePHex study and in the ePHex-OLE study will be described for the subjects enrolled in the ePHex-OLE study. Demographics will also be described for subjects included in the FAS of the ePHex study, but not participating in the ePHex-OLE study.

The listing of demographic data will include information on childbearing potential (for females only).

7.5.2 Medical history

Medical history will be coded by SOC and PT using MedDRA and presented as number/percentage of subjects in each SOC and PT per treatment group and overall for the FAS population. SOC and PT will be presented in descending order of frequency. If several SOC/PTs have the same number of frequencies, the SOC/PTs will be presented in alphabetical order. These data will also be listed on a per subject level. Note that medical history as collected for this study are medical events occurring before first dosing for ePHex-OLE but after the safety follow-up period in the ePHex study, as well as medical history from the ePHex that is still ongoing in the ePHex-OLE study.

For handling missing dates, see section [7.2](#).

7.5.3 Other (screening) data

Pregnancy tests will be listed for females of child-bearing potential only.

7.6 Statistical analysis primary and secondary endpoints

7.6.1 Primary endpoint

The primary efficacy endpoint is the change from baseline in kidney function (eGFR) after 12 and 24 months of open-label Oxabact treatment. The primary endpoint will be presented using the FAS population.

The primary analysis will be based on the 24-month data and using the baseline of the ePHex as primary baseline, while other time-points presented will be considered as supportive. A second analysis is done using the baseline of ePHex-OLE for the ePHex placebo subjects as baseline.

Change from baseline in kidney function (eGFR) will be calculated at each visit, using the two different baselines. Summary statistics of the measurements will be presented on a per-visit basis. Presentations will be per treatment group and overall.

To visualize the effects through time graphically, the following plots will be created:

- Individual plots will be created to visualize the course of eGFR values through time (including the ePHex values, as applicable). Both the actual values as well as change from baseline values will be presented.
- Mean \pm SE will be created to visualize the course of eGFR values through time (including the ePHex values, as applicable). Both the actual values as well as change from baseline values will be presented for the overall group and for both treatment groups, preferably in the same plot.
- Spaghetti plots per treatment group of the actual values will be created to visualize the group course of eGFR through time, using the same y-axis for visual comparison between groups. No spaghetti plots will be created for change from baseline. One plot will be created, using colors to discriminate both treatment groups (which combined will show the overall group).
- A plot presenting LS estimates \pm SE will be created, based on the mixed-effect repeated measures model stated below.

A statistical analysis will be performed using a mixed-effect repeated measures model (MRMM) on the change from baseline value at 12 and 24 months, with the following independent variables: treatment group, baseline eGFR value, time and time*treatment group interaction. If the assumption of normality is violated, a log transformation will be applied first (and a back transformation will be done on the results). SAS PROC MIXED (with the REML default) will be used for the analysis. The basic SAS code will be as follows.

```
proc mixed data=...;  
  class usubjid <time>;  
  model change=treatment time treatment*time baseline;  
  repeated time / subject=usubjid(treatment) type=...;  
run;
```

The time variable will preferably be the same as used for ePHex, to be able to make comparisons.

Considering the variability of eGFR, an AR(1) covariance matrix will be used in the model, which assumes that a correlation between two consecutive measurements is higher than between two measurements further apart in time. If the model does not converge, an unstructured (UN) covariance matrix will be applied, to allow variances and covariance to differ at and between measurements. As the use of an unstructured (UN) covariance matrix requires estimation of a larger number of variance and covariance parameters (and is thus computationally more intense), the model is likely not converge if AR(1) already did not converge. If that occurs, the structure will be adapted to respectively Toeplitz or Compound Symmetry (CS).

From this model, the comparison at 12 and 24 months will be extracted (both overall as well as per treatment group). Comparisons of other visits will be extracted as well and presented as secondary. The tables will display the LS means, SE, 95% CI for each visit and the p-values for the differences at 12 and 24 months.

In addition, since the model provides a test of difference in slopes using the proposed time-by-treatment interaction, treatment slopes and slope differences on change will be presented as well. Only the values after first open label treatment will be used for determination of the slopes.

As a sensitivity analysis for the primary endpoint, the same model will be used after applying a multiple imputation (MI) method for missing data under the missing at random assumption (MAR). Missing data patterns and covariates related to the missing data patterns will be examined and described. A total of 10 multiple imputations will be generated using predicted mean matching based on a monotone regression (in case the missing data pattern is monotone) or on a fully conditional specification regression (in case the missing data pattern is arbitrary and non-monotone). The predicted mean matching method imputes an observed value which is closest to the predicted value from the simulated regression model for each missing value. It ensures that imputed values are plausible and might be more appropriate than the regression method if the normality assumption is violated. The regression model will condition on observed values of the primary outcome measured at other time points (including baseline measurements) and possible other covariates that are related to the missing data pattern and/or primary endpoint.

The mixed-effect repeated measures model described above will be applied to each imputed dataset separately. The estimated parameters will be pooled using Rubin's combining rules. Only the primary comparisons at 12 and 24 months will be analysed using this approach.

The analysis above will be done under the assumption of missing at random (MAR). Since it concerns a supportive analysis of the descriptive statistics, no further analysis will be done to assess the robustness of the primary analysis to possible deviations from the missing at random (MAR) assumption.

As a secondary method of analyses corresponding to the MMRM above will be done using an ANCOVA model with treatment group, baseline/second baseline as covariates and change from baseline/second baseline in eGFR at 12 and 24 months as a dependent variable.

An additional statistical analysis using MRMM will be employed to evaluate the change in eGFR when on Oxabact treatment for a period of 12 months or 24 months, depending on when the subject actually received Oxabact for the first time (for O – O this is the start of treatment during the ePHex study, for P – O this is the start of treatment during the current study).

If the models cannot be run because of the small sample size of the study, either or not in combination with too many missing data, then analysis will be limited to descriptive statistics and graphical displays as described.

All the analyses described above for eGFR are based primarily on the Creatinine-based “Bedside Schwartz” for children and CKD-EPI 2009 equations² for adults. For subjects aged between 18 and 23 years (both inclusive) of age, the mean of the children and adult equation results will be calculated as described in the appendix referred in section 11.1).

In addition, supportive analyses based on the Cystatin-C based CKiD for children and CKD-EPI 2012 equations³ for adults (see section 11.1) will be carried out, and similar analyses and presentations as for the Creatinine-based “Bedside Schwartz”/ CKD-EPI 2009 equation will be done. For Cystatin-C based equations, no modification for subjects between 18 and 23 years will be performed.

For children, height values are collected at each visit, and therefore the additional supportive eGFR values will need to be adjusted on a per-visit basis accordingly.

Adults only have one height collected at baseline, and this will be used throughout. Age will need to be determined at each visit, if not collected. Given that for most subjects no full birth date will be available, an estimation of age will be used following section 7.2.

² Children: $eGFR=41,3 \times (\text{height} / S_{Cr})$, Adults: $eGFR=141 \times \min(S_{Cr}/\kappa,1)^\alpha \times \max(S_{Cr}/\kappa,1)^{-1,209} \times 0,993^{\text{age}} \times \gamma$, with S_{Cr} = serum creatinine (mg/dL), $\kappa = 0,7$ (females) or $0,9$ (males), $\alpha = -0,329$ (females) or $-0,411$ (males), $\gamma = 1,018$ (female) or $1,159$ (black) or 1 (otherwise), age in years and height in m.

³ Children: $eGFR=39,8 \times (\text{height} / S_{Cr})^{0,456} \times (1,8/S_{cys})^{0,418} \times (30/BUN)^{0,079} \times 1,076^{\text{male}} \times (\text{height}/1,4)^{0,179}$, Adults: $eGFR=135 \times \min(S_{Cr}/\kappa,1)^\alpha \times \max(S_{Cr}/\kappa,1)^{-0,601} \times \min(S_{cys}/0,8,1)^{-0,375} \times \max(S_{cys}/0,8,1)^{-0,711} \times 0,993^{\text{age}} \times 0,969^{\text{female}} \times 1,08^{\text{black}}$, with S_{Cr} = serum creatinine (mg/dL), S_{cys} = serum cystatine-C (mg/L), $\kappa = 0,7$ (females) or $0,9$ (males), $\alpha = -0,248$ (females) or $-0,207$ (males), BUN = Blood Urea Nitrogen (mg/dL), age in years and height in m.

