12.5.1 Change from Baseline in eGFR Supportive Analyses MRMM

A supportive additional analysis of the data may also be performed, whenever possible, using Mixed Effect Repeated Measures Model (MRMM) analysis based on the FAS with a model including fixed effect factors: treatment group (0 - 0; P - 0), baseline stratification factors at randomisation (PH type 2/3, not PH type 2 or 3 and baseline urinary oxalate excretion $\leq 1.87 \text{ mmol}/24\text{h}/1.73 \text{ m}^2$, not PH type 2 or 3 and baseline urinary oxalate excretion $\geq 1.87 \text{ mmol}/24\text{h}/1.73 \text{ m}^2$), week, and week-by-treatment interaction, and the following fixed effect covariates: baseline eGFR value.

An autoregressive of order 1 (AR (1)) variance covariance matrix will be used for the within subject variation in the MRMM model. In case there is a convergence problem the following variance covariance matrix structures will be used in the order of 1) unstructured, 2) Toeplitz, and 3) compound symmetry (CS). The first (co)variance structure which does not have convergence problem will be the one used for the analysis.

A descriptive comparison will be presented at 12 and 24 months in change from baseline between 0 – 0 and P – 0 treatment groups as measured by the treatment effect factor. Results will be summarised including LS mean change from baseline in eGFR at months 12 and 24 (SE) in both treatment groups along with treatment group difference (LS mean difference) and corresponding 95% confidence interval. The same results will be presented also for the other timepoints.

To describe if Oxabact treatment has a similar effect during the first 12 and 24 months in the O-O and P-O groups, a second MRMM analysis on change from baseline in eGFR in the O-O group and change from second baseline in the P-O group based on the FAS will be used with a model including fixed effect factors: treatment group (O-O; P-O), week, and week-by-treatment interaction, and the following fixed effect covariates: baseline eGFR (baseline for the O-O group and second baseline for the P-O group).

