12.5.2 Change from Baseline in eGFR Supportive Analyses

A secondary method of analyses, corresponding to the MRMM above, will be done using an ANCOVA model with treatment group, baseline/second baseline stratum, and baseline/second baseline as covariates and change from baseline/second baseline in eGFR at 12 and 24 months as a dependent variable. Supportive analyses based on AUC may also be performed and further described in the SAP.

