12.6 Key Secondary Endpoints

12.6.1 Total Plasma Oxalate

Change from baseline in total plasma oxalate concentration will be analysed similar to the primary endpoint. Total Pox observed minimum and maximum post baseline values and change from baseline will also be summarised and plotted. Additionally, a combined plot for key secondary endpoint total plasma oxalate and primary endpoint eGFR over time will be created using a double-axis display. This plot will be created for

each patient, but also a summary plot presenting both parameters' mean values over time per treatment group will be made.

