7.6.4 Subgroup analyses

Subgroup analyses using descriptive statistics of the following endpoints may be presented if considered feasible: change from baseline for eGFR, change from baseline for total and free plasma oxalate concentration, change from baseline for 24h urine oxalate excretion (non-centrifuged only), stone events incidence rate (as per adjudicated data) and change from baseline for speckle tracking and traditional echocardiography (limited to LVEF/GLS). Presentations will be done for each visit. Both baselines will be used. The analyses will be based on the following subgroups, provided the subgroups are sufficiently large (>2):

- Subjects with a baseline urinary oxalate excretion (non-centrifuged) above and equal to or below 1.87 mmol/L/24h/1.73 m² respectively (mean of the two values during screening/baseline of the ePHex study).
- Subjects above or equal to and below 18 years of age at baseline of the ePHex study.
- Subjects with a baseline eGFR above or equal to (\geq) and below ($<$) 60 ml/min/1.73m² respectively (mean of the obtained values during screening/baseline of the ePHex study calculated by the Schwartz/CKiD equation⁴), with correction for 18-23 years.
- Race.
- Gender.
- Progressors and non-progressors (see section 11.1) based on historical eGFR (i.e. eGFR prior to treatment start including the baseline/screening values of the ePHex study), using the Schwartz/CKiD equation.

⁴ The Schwartz CKiD 2009 creatinine-based “bedside Schwartz” equation for children (below 18 years of age) and 2009 creatinine-based CKD-EPI equation for adults.

For the subgroup analyses only the FAS population will be used. No formal testing of subgroups will be performed due to small sample sizes. No plots will be created.

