8 CHANGES FROM PROTOCOL AND OTHER RELEVANT REMARKS

The descriptive statistics on percent change from baseline in total plasma oxalate concentration, on subjects achieving 'near-normalization' of total plasma oxalate concentration (<10 µmol/L), and on the shifts to minimum and maximum values for total plasma oxalate concentration were not mentioned in the protocol, but added as these were considered relevant in the ePHex study.

Subgroup analysis based on type of PH (as per randomization for ePHex) will not be conducted due to the expected insufficient number of subjects in the subgroups.

The sensitivity analysis for the MRMM for eGFR will be done under the assumption of missing at random (MAR). Since it concerns a supportive analysis of the descriptive statistics with a small sample size, no further analysis will be done to assess the robustness of the primary analysis to possible deviations from the missing at random (MAR) assumption, and therefore the pattern-mixture analysis is removed from the SAP.

Furthermore, the regression analysis to determine slopes for eGFR, and the summary table and statistical thereof is excluded from the SAP, considering slopes are already determined based on a MRMM. Any apparent differences in slopes can best be assessed based on the individual slope results of the MRMM analyses and viewing the spaghetti and mean plots.

Any post-hoc analyses or changes in regards to the statistical analysis plan when performing the final analyses after data base lock, will be captured in a Note to File and used for the relevant sections in the clinical study report.

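### The SAP drops the ePHex randomisation stratum from the supportive eGFR and plasma oxalate models in which the protocol placed it, and does not list this as a change

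*SAP*

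**What the plan says.** **Protocol.** Section 12.5.1 lists among the fixed effects of the first supportive eGFR MRMM the "stratification factors at randomisation (PH type 2/3, not PH type 2 or 3 and baseline urinary oxalate excretion" at the 1.87 cut, which makes three levels. Section 12.5.2 specifies an "ANCOVA model with treatment group, baseline/second baseline stratum, and baseline/second baseline as covariates". Section 12.6.1 adds: "Change from baseline in total plasma oxalate concentration will be analysed similar to the primary endpoint". The second MRMM in 12.5.1, which counts from the start of Oxabact, has no stratum.

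**SAP.** Section 7.6.1 specifies the MRMM "with the following independent variables: treatment group, baseline eGFR value, time and" the time-by-treatment interaction, and the SAS model statement there has treatment, time, their interaction and baseline only. The multiple-imputation analysis reuses that model. The secondary method is an "ANCOVA model with treatment group, baseline/second baseline as covariates". Section 7.6.2 analyses total plasma oxalate with a similar MRMM.

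**Declared changes.** SAP section 8 records the added plasma oxalate summaries and the removal of the pattern-mixture analysis and of the per-subject slope regressions. It also states: "Subgroup analysis based on type of PH (as per randomization for ePHex) will not be conducted", because too few subjects are expected. It does not mention the stratum as a model term.

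**The concern.** The SAP states that it is written in agreement with protocol version 2, and section 8 itemises its departures. A reader would therefore take the models to match, and they do not.

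The comparison at stake is O-O versus P-O. Randomisation balanced the arms of ePHex within strata, but the extension contains only those who completed ePHex and went on, with 25% a year expected to drop out. If one group holds more subjects from a faster-declining stratum, a model without the stratum can attribute part of that to treatment order.

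With the PH-type subgroup also removed, no table listed in the SAP names PH type, so an imbalance in that factor has no planned display. Although the models are supportive, SAP 7.6.1 tabulates 95% confidence intervals and p-values for the differences at 12 and 24 months, and those figures will be read.

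**Working it through.** **1. Model terms side by side**

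| Model | Protocol | SAP |
|---|---|---|
| eGFR MRMM, from ePHex baseline | stratum included (12.5.1) | no stratum (7.6.1) |
| Multiple-imputation rerun of that MRMM | optional, no separate model given (12.11) | no stratum (7.6.1) |
| eGFR ANCOVA | stratum included (12.5.2) | no stratum (7.6.1) |
| Total plasma oxalate MRMM | stratum by reference (12.6.1) | no stratum by reference (7.6.2) |
| Second eGFR MRMM, from Oxabact start | no stratum (12.5.1) | no stratum (7.6.1) |

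The stratum stands in three protocol models and in no SAP model. The last row is not affected. The SAP lets other covariates into the imputation regression, but that does not put the stratum into the analysis model.

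**2. Who is compared.** SAP 2.4 gives 18 included. Protocol 4.4.1.8 and 11.5.3 give 25 randomised by June 2020. 18/25 = 72%.

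**3. Possible size of a bias.** Shift = (subjects in excess / group size) × (difference in yearly slope) × years. Take nine per group (18/2), two extra PH1 subjects in one group (an assumption), and three years from the ePHex baseline. Slopes are from Protocol 6.1.
- Average rates, PH1 −1.7 and PH2 −1.04 per year: 2/9 × 0.66 × 3 = 0.44 mL/min/1.73 m². Against the planned difference of 5 that is 9%.
- If those two are in the accelerated phase, −9 against −0.822 per year: 2/9 × 8.178 × 3 = 5.45.

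These are shifts in an unadjusted difference. The SAP models adjust for baseline eGFR, which may remove part of them. The range is too wide to give a usable estimate.

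**4. Does the stated power change?** Protocol Table 11 gives 0.97601 for a difference of 5, SD 3, 16 subjects and within-subject correlation 0.70. With m repeated measures, compound symmetry and a normal approximation, the variance factor is f = (1 + (m − 1) × 0.70)/m. The number m is not stated; m = 18 gives f = 12.9/18 = 0.7167 and reproduces all 12 cells. SE = 3 × √(0.7167 × (1/8 + 1/8)) = 1.270; 5/1.270 = 3.94; 3.94 − 1.96 = 1.98; power 0.976. The stratum is not an input, so the stated figure is the same with or without it.

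**5. What restoring the stratum costs.** Noncentral t, difference 5, SD 3, between-subject df = N − 3 without the stratum and N − 5 with it, stratum assumed to explain no variance:

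| N in total | Critical t | Power, m = 18 | Power, single visit |
|---|---|---|---|
| 16 | 2.160 to 2.201 | 0.953 to 0.947 | 0.868 to 0.858 |
| 12 | 2.262 to 2.365 | 0.858 to 0.831 | 0.729 to 0.698 |
| 9 | 2.447 to 2.776 | 0.688 to 0.601 | 0.549 to 0.473 |

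If the stratum explains 20% of the variance, single-visit power with it is 0.923 at N = 16 (0.868 without) and 0.557 at N = 9 (0.549 without). Break-even at nine completers is therefore a little under 20%.

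**The case against.** The strongest defence is that a smaller model is sensible here. Nine completers are planned, and two degrees of freedom cost 8 to 9 points of power at that size if the stratum explains nothing. SAP section 8 already expects too few subjects by PH type, so one level may be nearly empty. The primary analysis is descriptive, the protocol makes the MRMM conditional on feasibility, and the SAP calls any p-value indicative only. Baseline eGFR stays in the models. Urinary oxalate and progressor subgroups are planned where feasible, with their numbers shown in the disposition summary. All of this stands as a reason why the sponsor might choose the reduced model. It does not explain why the choice is undeclared: the small-numbers reason in section 8 covers only a subgroup analysis.

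Three stronger readings are tempting and not supported.
- A reader might infer that the SAP replaced the strata with a two-way cut in a wrong unit. The subgroup "above and equal to or below 1.87 mmol/L/24h/1.73 m² respectively" stands in the same form in Protocol 12.8, alongside the strata. It cannot substitute for them, since PH type 2 and 3 subjects fall on both sides of it, but the SAP did not introduce it.
- A reader might take Protocol Table 4 to show that the strata are the strongest predictors of eGFR change. The table is univariate and concerns ESRD. PH1 stands out (HR 13.17), but the top urinary oxalate quartile (HR 3.40) sits beside a null continuous effect (HR 1.13, p = 0.20). Reading the eGFR hazard ratio of 0.96 as per 1 mL/min, a baseline 30 mL/min lower gives 0.96^−30 = 3.4, and eGFR is kept in the model.
- A reader might assume a stratum 5 to 10 mL/min/1.73 m² worse and obtain a shift of 1.1 to 2.2, or 22 to 44% of 5. No such difference between strata is given in the documents.

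Nor is all the non-entry self-selection: France took part in ePHex and is not among the planned extension countries.

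**Conclusion.** The point holds as a documented mismatch. The SAP removes a pre-specified randomisation stratum from the eGFR MRMM, the eGFR ANCOVA and the total plasma oxalate MRMM, applies the reduced model to the multiple-imputation rerun, and gives no notice or reason. Its weight is moderate: the models are supportive, there is no formal testing, and no stated power or error rate changes.

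Whether the omission biases O-O versus P-O depends on the stratum counts by group and on how fast each stratum declines, and the documents give neither. The 0.4 mL/min/1.73 m² figure rests on an assumed two-subject imbalance and on published average slopes; it is an illustration.

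Separately, and minor: the /L in the unit of the urinary oxalate subgroup is a slip shared by both documents. The strata and Table 4 use mmol per 24 h per 1.73 m².

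**What to change.** - Restore the three-level stratum, as recorded at ePHex randomisation, as a fixed effect in the eGFR MRMM, its multiple-imputation rerun, the ANCOVA and the total plasma oxalate MRMM. Set a rule for pooling sparse levels before unblinding, and show the reduced model beside it.
- If the sponsor prefers the reduced model as the main one, declare and justify that in SAP section 8 and report the stratified model beside it where it can be fitted.
- In either case, tabulate stratum by O-O and P-O.
- Leave the second MRMM as it is.
- Correct the subgroup unit to mmol/24h/1.73 m² in SAP 7.6.4, Protocol 12.8 and the protocol synopsis.

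The work is one class variable from the ePHex randomisation data, one table and a few lines of text. The statistical price is two degrees of freedom: about 1 point of power or less at 16 subjects, and about 8 to 9 points at nine completers if the strata explain no variance. Showing both models lets the reader see that trade-off.

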2.4 Sample size

Approximately 16 subjects were anticipated to be included in the study, dependent on the number of subjects who complete ePHex and chose to participate in ePHex-OLE. It is anticipated, based on a drop-out rate of 25% per year, that there will be approximately 12 subjects completing the 12-month visit, and 9 subjects completing the 24-month visit.

Assuming a difference between treatment groups in eGFR change at month 24 from baseline of 5 mL/min/1.73 m² with an SD of 3, the power will be greater than 90% with a sample size of 16 subjects. This power calculation is done using a repeated measures model in a two-sided approach with $\alpha=5\%$, a 1:1 allocation ratio for a total of 16 subjects, and assuming a within subject correlation of 0,70.

At the time of signing off the Statistical Analysis Plan it is known that 18 subjects were included.

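### The multiple-imputation check of the eGFR model does not require treatment group as a predictor and matches on about 10 observed month-24 values, so it can understate a true O-O versus P-O difference

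*SAP*

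**What the plan says.** SAP 7.6.1 gives multiple imputation under missing at random (MAR) as the sensitivity analysis of the eGFR mixed model (MRMM): "A total of 10 multiple imputations will be generated using predicted mean matching", built on a monotone regression or a fully conditional specification according to the missing-data pattern. The method "imputes an observed value which is closest to the predicted value from the simulated regression model for each missing value". On predictors the text reads "The regression model will condition on observed values of the primary outcome measured at other time points (including baseline measurements"), followed by "and possible other covariates that are related to the missing data pattern and/or primary endpoint". Treatment group is not named. The number of donors, the visits used and the scale imputed (raw eGFR or change) are not stated in that section.

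The mixed model of the same section is then fitted to each completed dataset, with "treatment group, baseline eGFR value, time and time*treatment group interaction" as its independent variables. "The estimated parameters will be pooled using" Rubin's rules, and only the 12- and 24-month comparisons are handled this way.

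On numbers, SAP 2.4 expects "9 subjects completing the 24-month visit" out of 16, from 25% drop-out per year, and adds: "At the time of signing off the Statistical Analysis Plan it is known that 18 subjects were included".

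Protocol 12.11 allowed LOCF, multiple imputation and a pattern-mixture model. SAP 8 removes the pattern-mixture analysis, SAP 7.6.1 plans no LOCF, and it rules out further work on departures from MAR. The multiple imputation is the only missing-data sensitivity analysis left.

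**The concern.** An imputation model should contain the terms that the analysis model goes on to estimate. If treatment group is left out, a missing value is predicted as though O-O and P-O subjects followed one common relation between earlier and later eGFR, and the imputed values move toward the average of the two groups. Earlier eGFR carries part of the group difference, so the pull is partial. It is strongest when the groups separate late.

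Matching adds a second pull. With about 10 observed month-24 values, about 5 per group, the closest donor may belong to the other group, and no imputed value can lie beyond the observed ones.

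The MRMM and the imputation rest on the same MAR assumption and should agree apart from noise. A smaller difference in SAP Table 14.2.6 would be read as fragility to missing data when it came from the imputation method. Month 24 is the primary time point in SAP 7.6.1, and it is where the loss is largest.

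**Working it through.** **Inputs from the documents.** True month-24 difference 5, SD 3, within-subject correlation 0.70, 1:1 allocation (SAP 2.4, Protocol 12.2); 18 subjects, 25% drop-out per year, 10 imputations.

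**1. The plan's own figure.** The documents give no figure for the imputation, so the power figure was used to check the inputs. Power = Φ(δ / (s·√(2/8)) − 1.96), with s = SD·√((1 + (m − 1)·0.7)/m). With m = 18, s = 3·√(12.9/18) = 2.540, and 5/(2.540 × 0.5) − 1.96 = 1.98, giving 0.976. Protocol Table 11 prints 0,97601, and all 12 cells agree. The value m = 18 is not stated and was found by fitting; m = 1 gives 0.915.

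**2. Observed values available as donors.** Month 12: 18 × 0.75 = 13.5. Month 24: 18 × 0.75² = 10.1, about 5 per group, so 43.75% are missing. With 16 subjects the counts are 12 and 9.

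**3. Simulation.** About 370 to 390 usable trials per setting, with visits at months 0, 6, 12, 18 and 24. Drop-out is monotone and completely at random. Each missing visit is imputed from baseline and up to two preceding visits. ANCOVA on change stands in for the MRMM, and estimates are averaged over 10 imputations. Assumed, because the documents do not give them: baseline eGFR mean 60 and SD 18, compound-symmetric or AR(1) correlation, and the course of the difference (constant, linear over 36 months, emerging in the extension, or late).

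Examples, imputing the change score. Each row is its own set of trials, with simulation standard error 0.07 to 0.12:

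| Course of difference | Imputation | Treatment in imputation model | Full data | After imputation | Change |
|---|---|---|---|---|---|
| Linear | Nearest donor | no | 5.14 | 3.49 | −32% |
| Linear | Nearest donor | yes | 5.11 | 4.37 | −14% |
| Linear | Regression | yes | 4.87 | 5.08 | +4% |
| Emerging, AR(1) | Nearest donor | no | 4.95 | 2.94 | −41% |
| Emerging, AR(1) | Nearest donor | yes | 4.96 | 4.26 | −14% |
| Emerging, AR(1) | Regression | no | 5.07 | 3.36 | −34% |
| Emerging, AR(1) | Regression | yes | 5.09 | 5.10 | 0% |
| Late, AR(1) | Nearest donor | no | 4.88 | 2.78 | −43% |
| Late, AR(1) | Nearest donor | yes | 5.09 | 4.42 | −13% |
| Late, AR(1) | Regression | no | 5.03 | 2.73 | −46% |
| Late, AR(1) | Regression | yes | 5.05 | 4.96 | −2% |

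Over all settings, on raw and change scales:
- nearest donor without treatment: 2.7 to 4.4 (14% to 45% below full data);
- nearest donor with treatment: 4.2 to 4.7 (7% to 16% below);
- regression with treatment: 4.9 to 5.3 (within about 4%).

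Most of the loss comes from leaving out treatment, since regression without it is also low. Matching adds a smaller loss of its own. A second simulation on the same planning inputs gave 3.0–3.7, 4.4–4.5 and 4.9–5.1 for these three methods, against 4.9–5.1 on full data.

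**4. Limits of the effect (nearest donor, treatment left out).** At month 12, a true 5 is estimated as 4.5–4.8 and a true 3.3 as 2.7–3.0. With no true difference the month-24 estimate is 0.06. With 16 subjects the linear case gives 3.48.

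**5. Number of imputations.** Linear course, 10 versus 50 imputations:
- nearest donor without treatment: 3.49 versus 3.46 (Monte Carlo standard error 0.25 versus 0.12);
- nearest donor with treatment: 4.37 versus 4.45 (0.30 versus 0.15);
- regression with treatment: 5.08 versus 4.97 (0.63 versus 0.28).

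Relative efficiency of 10 imputations is 1/(1 + 0.4375/10) = 0.958 if the fraction of missing information equals the fraction missing.

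**The case against.** The best defence is the open clause: treatment is a term in the model for the primary endpoint, so a covariate related to that endpoint may be included. This stands. A reader might infer that the SAP omits treatment and is therefore biased, but the text does not support that. It leaves the choice open. The clause does not fully rescue the plan, because the stated matching rule still loses about 7% to 16% with treatment included.

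Four other stronger readings go beyond the documents:
- Ten imputations do not contribute to the shrinkage; they add noise.
- Matching from 5 donors gives worse figures (2.6–3.6 without treatment, 3.4–3.9 with it), but the SAP states no donor number and its wording points to the single closest value.
- Using every visit would need 11 coefficients at month 24 (intercept, baseline and nine earlier extension visits) for about 10 observed values. The SAP says other time points, not all of them, and falls back on descriptive output if the models cannot be run.
- About 10 donors describes month 24, not month 12.

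The SAP also gives a reason for matching: plausible values and less reliance on normality. That is a fair trade-off to weigh. Finally, this is a check on a supportive model in a descriptive study without formal testing, and SAP 7.1 drops statistical analysis if ePHex is negative and the extension closes early. No main conclusion of the trial depends on it.

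**Conclusion.** The point holds in conditional form. If the groups truly differ and treatment is left out, nearest-donor matching turns a month-24 difference of 5 into about 2.7 to 4.4. If treatment is put in, matching from about 10 observed values still leaves the estimate about 7% to 16% low. Month 12 loses less, and with no true difference nothing is shrunk.

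The sizes rest on the plan's difference, SD, correlation and drop-out rate, and on assumptions about the course of the effect, the drop-out mechanism and the visits used. The direction was the same in every setting with a month-24 difference of 5. The consequence is limited to a sensitivity table that could contradict the MRMM for reasons unrelated to the missing-data assumption. That merits a correction to the SAP but does not threaten the study.

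**What to change.** In SAP 7.6.1:
- Make treatment group a mandatory predictor in the imputation model.
- Limit the other predictors to baseline eGFR and the one or two preceding visits, and list them. With treatment and an intercept that is 4 or 5 coefficients for about 10 observed month-24 values.
- Use regression imputation instead of matching, and state the scale imputed.
- If matching is kept, state the number of donors and report the expected shrinkage alongside the result.
- Separately, raise the imputations from 10 to 50–100. For regression imputation the Monte Carlo standard error falls from 0.63 to 0.28 at 50, and to about 0.28 × √(50/100) = 0.20 at 100. This does not change the shrinkage.

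Imputing separately within each group is not advised: it leaves about 5 observed month-24 values per group for 3 or 4 coefficients.

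The cost is a few lines of SAP text and trivial computing time. Regression imputation can give values outside the observed range and loses some robustness to non-normality. Its estimates also vary more: in the linear case with 50 imputations the SD across trials was 2.0, against 1.8 for nearest-donor matching with treatment.
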